3.1.2. Safety Endpoints

Safety will be assessed through review of Adverse Event (AE) reports and unanticipated adverse device effects. Safety outcomes will be assessed at the interim visits and the end of study visit.

4. STUDY OVERVIEW

4.1. Study Design

Part A of this trial is a multi-center, prospective, double-blinded, sham-controlled, randomized clinical trial conducted on subjects with painful diabetic distal symmetric peripheral neuropathy. Part B of this trial is a 8-month single-arm, open-label, active treatment extension period upon completion of Part A (the SAP for Part B is laid out in a separate document).

Eligible subjects will include those between 22 and 79 years of age with documented Type 1 or Type 2 diabetes having persistent pain related to diabetic neuropathy in the lower extremities, despite previous treatment(s). Subjects will be assessed with the Toronto Clinical Neuropathy Score at screening, to evaluate the severity of peripheral neuropathy for inclusion.

Eligible subjects will be entered into a 14-day electronic patient-reported outcome (ePRO) diary run-in period to collect average baseline pain scores related to their diabetic neuropathy in the lower extremities, diary compliance, and analgesic consumption (maintenance and prn prescribed peripheral neuropathic pain medication pill counts). Subjects will collect ePRO data each morning around the same time during the run-in period. Only those subjects having a mean pain intensity in the lower extremities of ≥ 4 and ≤ 9 on an 11-point numeric pain rating scale (NPRS) and a diary compliance score of $\geq 70\%$ during the 14-day run-in period will be eligible.

Subjects will return to the clinic at Baseline (Day 0) for review of eligibility, diary compliance, average baseline diabetic neuropathic pain score of ≥ 4 and < 9 (calculated as the average of the last 7 days preceding the enrollment visit), and review of stable analgesic pain consumption profile during the 14-day run-in period. Qualified subjects based on diary compliance and average pain score will be randomized 1:1 (active: sham) and will be instructed to self-treat twice daily (morning and evening; $8am \pm 2$ hours and $8pm \pm 2$ hours) for 120 days. Subjects will record electronic patient-reported outcome (ePRO) data following each morning treatment for 120 days. Subjects consenting to distal thigh and distal leg skin biopsies during the Screening visit will have biopsies collected and sent to the central laboratory for assessment. All subjects will have a baseline Skin Perfusion Pressure (SPP), Sural Nerve Conduction Studies (NCS), Quantitative Sensory Testing (QST), and will also complete the Work Productivity and Activity Impairment Questionnaire (WPAIQ) and NeuroQoL.

4.2. Study Treatment

The study device is the PROVANT® Therapy System (aka Dual Pad DPN Therapy). The active device will deliver dual field pulsed electromagnetic field energy in the radiofrequency range. The active treatment and inactive sham devices will be identical in appearance and all other physical characteristics in order to maintain the blinding of the treatment. Each device will be identified with a unique kit number.

4.3. Sample Size Justification

This is a Phase III study with a sample size of 170 patients (85 per treatment group). The sample size for the trial has been set at 170. Based on a previously conducted clinical trial assessing the efficacy and safety of the Provant Therapy System in a similar population, the mean \pm standard

November 7, 2018

deviation change in the NPRS from baseline to 60 days was 1.79 ± 1.83 units. The data are derived from the open-label, single arm part of the trial in which all subjects received PEMF. Assuming a placebo effect of 40% results in an assumed between group difference of 1.07 units. Based on alpha = 0.05 and 90% power, a sample size of 62 patients per treatment group would be needed based on a two-sided sample t-test for the NPRS. A total sample size of 162 was estimated based on enrolling 1.3 times the target sample size of 124 patients (124 * 1.3 = ~162).

4.4. Estimated Duration of Subject Participation, Withdraw and Followup

Subjects will be on study for approximately 12 months (4 months in Part A and 8 months in Part B). If a subject is withdrawn from study participation, the subject's enrollment in the study will terminate, study device application will be discontinued and no further data will be collected on the subject. Efforts will be made to perform all assessments scheduled for the Month 4 Visit (Day 121) prior to subject withdrawal in Part A, and Month 12 Visit (Day 361) prior to subject withdrawal in Part B.

A subject may be withdrawn from further study participation under the following circumstances:

- At the subject's request.
- Noncompliance with the protocol by the subject.
- Adverse Event (decision to be removed from study made by either the investigator or subject). The investigator must notify the sponsor immediately if a subject is withdrawn because of an AE.
- Decision by the investigator or sponsor that termination is in the subject's best medical interest or administrative decision for a reason other than that of an AE.
- Request for withdrawal by the subject for reasons other than an intolerable AE.
- Lost to follow-up, as determined by failure to respond to at least 2 telephone calls followed by certified letter sent to the subject's last known address. All attempts to contact the subject must be documented in the subject's source documents.

5. SCHEDULE OF ASSESSMENTS

The schedule of assessments is presented in Appendix A of the protocol.

6. ANALYSIS POPULATIONS

The primary population for assessing efficacy and safety will be the Intent to Treat (ITT) Analysis Set, defined as all subjects who were enrolled into the study and issued a study device.

A secondary analysis of the individual efficacy endpoints will be conducted using the Per Protocol (PP) Analysis Set, defined as all subjects who were enrolled and their compliance for using the study device was $\geq 70\%$. For the specific tables of the individual efficacy endpoints generated based on the PP analysis dataset, an x will be added to the table number for differentiation.

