4.18 Protocol Adherence

If an investigator has deviated from the protocol in order to eliminate an immediate hazard to subjects or for other inevitable medical reasons, the investigator shall document all such deviations, including the reasons thereof, and immediately submit the documentation to the sponsor and to the IRB if required.

Deviations from the protocol including violations of inclusion/exclusion criteria will be assessed as "minor" or "major". Deviations will be defined prior to un-blinding.

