4.19 Concomitant Medications

All concomitant drug and non-drug treatments as well as the frequency of administration and indication for the treatment will be recorded in the subject's chart. Additions and/or changes to the subject's therapeutic regimen (agent, dose, frequency of administration) for treatment of diabetic peripheral neuropathy pain (other than the introduction of PEMF therapy) will not be allowed through Day 360 of the study. Subjects will be allowed to continue administration of prn medications if they were added and taken at least 30 days prior to Screening.

It is important to record the reason why each analgesic is being taken by the subject, specifically analgesics taken for treatment of pain associated with diabetic neuropathy. The analgesics taken for diabetic neuropathy will be entered in to the ePRO system for the subject to enter the number of pills taken for each one daily through 120 days, at Months 5, 6, 7, 9, 10, and 11 phone calls, during the one week of ePRO assessments prior to Months 6, 8, 10, and 12 visits, and at the Month 8 and 12 on site visits. Analgesics taken for other reasons, e.g., headache, will be collected through recording of concomitant medications in the subject's chart.

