4.19.2 Prohibited Medications/Treatments

The following medications and therapeutics are prohibited throughout the study:

- Systemic steroids or topical steroids on the lower extremities
- Transcutaneous electrical neurostimulators (TENS units)
- Implanted neurostimulators
- Local injections
- Intrathecal infusion
- Acupuncture
- Surgery

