7. STATISTICAL CONSIDERATIONS

The statistical analysis plan for this study will be described in detail in a separate Statistical Analysis Plan (SAP). The initial phase of this study is defined as *Part A* and represents the randomized double-blind portion of the study. Part B is the open-label extension phase where all subjects will receive active therapy.

The primary population for assessing efficacy and safety will be the *Intent to Treat (ITT) Analysis Set*, defined as all subjects who were enrolled into the study and issued a study device.

A secondary analysis of the individual efficacy endpoints will be conducted using the *Per Protocol* (*PP*) *Analysis Set*, defined as all subjects who were enrolled and completed \geq 70% use in treating with the study device.

Subjects will complete a 14-day run in period to obtain an average over the last 7 days in the runin period to obtain the NPRS score for qualification. Once the subject is determined to be eligible, the subject will be enrolled and randomized 1:1 to either an active or inactive sham device and become part of the *ITT and PP sets*.

Subjects in the *ITT and PP sets* will be instructed in the use of the devices for 120 days in the home environment. At months 1, 2, and 3 subjects will return to the clinic to complete PGI and review of adherence to treatment and diary entries. At month 3, subjects will return for completion of the WPAIQ, NeuroQoL and SPP measurements. Subjects will return to the clinic at day 121 for final evaluation and to complete the questionnaires, SPP, QST, and NCS.

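### The Per Protocol set tests device use only: subjects with barred analgesic changes or prohibited treatments such as TENS stay in it, and the planned deviation grading feeds no analysis set

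*SAP*

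**What the plan says.** **Definition.** SAP 6 describes PP as "all subjects who were enrolled and their compliance for using the study device was" at least 70%. Protocol 7 has it "defined as all subjects who were enrolled and completed" at least 70% use. Neither adds a second condition.

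**Role.** In the SAP: "A secondary analysis of the individual efficacy endpoints will be conducted using the Per Protocol (PP) Analysis Set". ITT is the primary population in both documents.

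**What subjects may not do.** Protocol 4.19 states that additions or changes to the regimen "for treatment of diabetic peripheral neuropathy pain (other than the introduction of PEMF therapy) will not be allowed" through Day 360. Protocol 4.1 tells subjects not to introduce new analgesic medications or therapies through Day 180. The two dates need reconciling, but either covers all of Part A. Protocol 4.19.2 opens with "The following medications and therapeutics are prohibited throughout the study" and lists TENS, local injections, acupuncture, steroids and surgery, among others.

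**Deviation grading.** Protocol 4.18: "Deviations from the protocol including violations of inclusion/exclusion criteria will be assessed as" minor or major, with definitions fixed before unblinding. The criteria appear in neither document.

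**The concern.** The endpoint is self-reported pain in people who continue background analgesics, so a barred analgesic change or a prohibited pain treatment is an obvious route to a distorted contrast. Readers expect a set called Per Protocol to exclude such subjects. This one keeps all of them who reach 70% device use.

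Among those subjects, ITT and PP therefore carry the same distortion. If the two analyses agreed, a study report could present this as evidence that the result does not depend on departures from the protocol. The comparison would support that for device non-use only. The grading in Protocol 4.18, which could supply the missing condition, is planned but goes unused.

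**Working it through.** **1. Is there any route out of PP other than device use?**

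- Protocol 4.18: deviations are graded, but no text in either document links the grade to an analysis set. The disposition table in SAP 8 has no row for deviations.
- Protocol 5 and SAP 4.4: noncompliance is a ground on which a subject may be withdrawn. It is discretionary, and neither section says that a withdrawn subject leaves PP.
- SAP 11: the primary model has baseline pain as covariate, with site added to assess poolability. The MMRM adjusts for baseline, week, treatment by week and patient. SAP 7.1 adds only baseline variables. None of these handles analgesic changes after randomisation.
- SAP 12.2: analgesic and rescue doses go into listings and descriptive Tables 14.1.13 and 14.1.14.

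For barred analgesic changes and prohibited treatments, no text removes the subject from PP.

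**2. Eligibility violations.** Protocol 3.5 makes meeting every eligibility criterion a condition of being enrolled, and PP is limited to enrolled subjects. Read literally, violators fall outside PP, and outside ITT, which uses the same word. Protocol 4.18 nevertheless expects eligibility violations to be found and graded. The documents do not settle the matter.

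**3. Other inconsistencies in the definition.**

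- Protocol 7 also says that each randomised subject joins both the ITT and PP sets, before any usage is known. That contradicts the 70% condition. The synopsis mentions only ITT at this point.
- Protocol 4.17 equates full Part A adherence with a usage report of 120. Treatment twice daily for 120 days is 2 × 120 = 240 sessions. The 70% cut is 0.70 × 120 = 84 on one count and 0.70 × 240 = 168 on the other; 84/240 = 35%. SAP 10.1 gives no denominator.

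**4. The plan's sample size, as a reference point.** Inputs from SAP 4.3: difference 1.07, SD 1.83, two-sided alpha 0.05, power 90%.

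n per arm = 2 × (1.960 + 1.282)² × (1.83/1.07)² ≈ 61.5, so 62. This matches the stated 62, with power 0.902. An exact t-test gives 62.4, and power 0.898 at 62.

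**5. Possible size of the distortion.** The rates and analgesic effects are assumptions.

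Shift = (fraction of sham with added analgesic − fraction of active) × extra pain reduction.

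- A 10-percentage-point imbalance worth 1 to 2 points: 0.10 × 1 = 0.1 to 0.10 × 2 = 0.2. Dividing by 1.07 gives 9% to 19%.
- Excess in sham: the difference falls to 0.97 or 0.87, and power at 62 per arm to 84% or 75%.
- Excess in active: the apparent difference rises to 1.17 or 1.27.
- Wider range, 5% to 30% excess in sham and 1 to 2 points: shift 0.05 to 0.60, difference 1.02 down to 0.47, power 87% down to 30%.

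**6. Cost in power of a stricter PP set.** This starts from 85 per arm and assumes that the difference and SD are unchanged.

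| Removed from PP | Left per arm | Power |
|---|---|---|
| 10% | 76.5 | 95% |
| 20% | 68 | 93% |
| 30% | 59.5 | 89% |
| 40% | 51 | 84% |

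**The case against.** The best defence is that neither document says PP is meant to test co-treatment. A set built on device adherence is a legitimate, narrow choice, and background medication is examined separately through daily ePRO pill counts and dose tables by arm. That stands as a defence of the set's content. It does not defend its name, and the dose tables are descriptive, so they do not show how the treatment contrast would change.

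Four stronger readings are tempting, and the documents do not support them:

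- **Eligibility violators certainly remain in PP.** Protocol 3.5 points the other way; the question is open.
- **PP is the only secondary look at efficacy.** Protocol 7.1 also defines Completers and End of Study sets and missing-data sensitivity analyses, and SAP 7.2 adds a last-observation analysis. These depend on data availability, however, not on deviations.
- **More analgesic use in sham could explain a positive result.** It would shrink the difference. Only an excess in active could inflate it.
- **A given number of subjects is affected.** No deviation rate is stated. Applying an assumed rate to all 170 would also presume that every deviator reaches 70% use and that none is withdrawn.

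It is also fair to object that excluding subjects for analgesic changes selects on an event after randomisation that pain itself may drive, which can bias the contrast. Existing prn analgesics are permitted and would remain in any PP set. Both objections stand and limit what a stricter PP set can show.

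**Conclusion.** The point holds for barred analgesic changes and prohibited treatments: under the stated rule, subjects with these in Part A stay in PP if they reach 70% use. ITT and PP agreement would then speak to device non-use alone. For eligibility violations the documents conflict, and Protocol 3.5 and 4.18 must be reconciled.

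The size is unknown. The shift of 0.1 to 0.2 NPRS points rests on an assumed 10-percentage-point imbalance and an assumed analgesic effect of 1 to 2 points, and its direction depends on which arm has the excess. The primary ITT analysis is unchanged, so this is a defect in a supportive analysis. It should be corrected before unblinding, because exclusions chosen afterwards would have little credibility.

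**What to change.** 1. In SAP 6 and Protocol 7, define PP as ITT subjects with at least 70% device use and no major deviation in Part A. Draw the majors from the protocol's own prohibitions, limited to those that bear on pain assessment. Taking the whole of Protocol 4.19.2 would be too broad: it lists surgery without qualification, while Exclusion 9 tolerates minor day procedures. Finalise the list under Protocol 4.18 before unblinding, and report exclusions by arm and reason. If the sponsor prefers the present rule, relabel the set as device-adherent.
2. Remove the Protocol 7 statement that puts every randomised subject in PP. Reconcile Protocol 3.5 with 4.18 on eligibility violators. Reconcile the count of 120 in Protocol 4.17 with the 240 planned sessions, and state the denominator for the 70%.
3. Keep PP supportive and add an ITT sensitivity analysis that accounts for analgesic changes after randomisation, with its rule for scores recorded after a change written in advance. The daily ePRO pill counts supply most of the data. Because the ePRO list is filled from medications already identified, newly started drugs should also be checked against the concomitant medication record.

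The cost is a short definition and list, one added analysis and a somewhat smaller PP set. At 20% removed, 68 per arm would still give about 93% power under the planning assumptions. No new data collection is needed.

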7. ANALYSIS CONVENTIONS

Post-text tables and listings will be prepared in accordance with the current ICH Guidelines. The header of each table and listing will include the sponsor's name and the study number. The information and explanatory notes to be provided in the "footer" or bottom of each table and listing will include the following information:

- 1. Date and time of output generation.
- 2. SAS® program name, including the path that generates the output.
- 3. Any other output specific details that require further elaboration.

In general, tables will be formatted with a column displaying findings for all subjects combined. Row entries in tables are made only if data exist for at least one subject (*i.e.*, a row with all zeros will not appear). The only exception to this rule applies to tables that list the termination status of subjects (*e.g.*, reasons for not completing the study). In this case, zeros will appear for study termination reasons that no subject satisfied. The summary tables clearly indicate the number of subjects to which the data apply and unknown or not performed are distinguished from missing data. Tables, listings, and figures will provide the units of measurement, unless not applicable.

Results recorded at single times during the study will be presented using the *Level 1* display for the *ITT population*; the example structure is presented below.

Baseline Parameters	Active Provant Treatment	Sham Provant Treatment	Overall
Age N Mean Standard Deviation Median Minimum, Maximum Values			
Gender • Male (N [%]) • Female (N [%])			

The *Level 2* display will be used for summarizing the incidence of AEs. An example of the layout for AEs by severity is presented below.

Adverse Events	Active Provant Treatment	Sham Provant Treatment	Overall
Reported Term			
Severity			

The Level 3 display will be used for summarizing the parameters recorded multiple times during Part A of the study. An example of the layout is presented below; rows will be repeated for visits conducted at each month.

Parameters	Observation Time	Active Provant Treatment	Sham Provant Treatment
 N Mean Standard Deviation Median Minimum, Maximum Values 	Enrollment (Baseline) Visit		
 N Mean Standard Deviation Median Minimum, Maximum Values 	Month 4 Visit		
 N Mean Standard Deviation Median Minimum, Maximum Values 	Month 4 Visit Minus Baseline		

The Level 3 displays will report the paired results for the change from the baseline through Month 4. For example, if 18 subjects complete the baseline evaluation and 16 subjects complete the Month 4 visit, the difference (Month 4 minus Baseline) will contain 16 subjects.

Supportive individual subject data listings will be sorted and presented by subject number and visit date, if applicable. Listings will also include the number of days relative to the initial study treatment (active or sham).

Specific algorithms are discussed for imputing missing or partially missing dates, if deemed appropriate, under specific data topics. Imputed or derived data will be flagged in the individual subject data listings. Imputed data will not be incorporated into any raw or primary datasets. The imputed data will be retained in the derived / analysis datasets.

The total duration for a subject *on-study* will be calculated as the difference between the date of initial study treatment (active or sham) and the last day of observation plus 1 day. All calculations for defining the duration on-study will follow the algorithm DURATION = [STUDY COMPLETION OR WITHDRAW DATE – INITIAL TREATMENT DATE + 1].

This section details general conventions to be used for the statistical analyses. The following conventions will be applied to all data presentations and analyses.

- Summary statistics will consist of the count and percentage in each level for categorical variables, and the sample size (n) mean, median, standard deviation (SD), minimum, and maximum values for continuous variables.
- All mean and median values will be formatted to one more decimal place than the measured value. Standard deviation values will be formatted to two more decimal places

than the measured value. Minimum and maximum values will be presented with the same number of decimal places as the measured value.

- The number and percentage of responses will be presented in the form XX (XX.X%).
- All probability values will be rounded to four decimal places. All p-values that round to 0.0000 will be presented as '<0.0001' and p-values that round to 1.0000 will be presented as '>0.9999'. P-values <0.05 will be considered to be statistically significant.
- All summary tables will include the analysis population sample size (i.e., number of subjects).
- Study Day 1 is defined as the day the subject receives their initial exposure to the active study device. All *study days* are determined relative to the day of initial treatment with the study device.
- Baseline values will be defined as those values recorded closest to, but prior to, the first active study treatment.
- Change from baseline will be calculated as follows:
 - Change = Post-baseline value baseline value.
- Date variables will be formatted as DDMMMYYYY for presentation.
- Tables, figures, and listings will be presented in landscape orientation.
- SAS® Version 9.2 or higher will be the statistical software package used for all data analyses.
- All data from this study will be presented in listings. All listings will be sorted by subject number and visit date, as applicable.
- Table and listing numbering will follow ICH guidelines for post-text table and listing numbering.

